### 10.1.7 Grading of AEs

The grading of AEs in this trial will be carried out on the basis of the 5-grade scale defined in the CTCAE v4.03:

Grade 1:	Mild
Grade 2:	Moderate
Grade 3:	Severe
Grade 4:	Life threatening or causing disablement
Grade 5:	Death

The grading of all AEs listed in the CTCAE v4.03 will be based on the information contained therein. The grading of all other AEs, i.e., those, which are not listed in the CTCAE v4.03 will be performed by a responsible investigator, based on definitions given above.

Clarification of the difference in meaning between "serious" and "severe":

The terms “serious” and “severe” are not synonymous. The term ‘severe’ should be used to describe the intensity (severity) of a specific event; the event itself, however, may be of relatively minor significance (such as severe headache). This is not the same as “serious”, which is based on the existence of one of the above mentioned seriousness criteria.

If the intensity of AEs worsened or if there are different CTC-grades during the course of trial, the highest intensity should be documented generally. If applicable, dependent on the AE, one AE for each intensity level should be recorded.

In case of lab parameters of CTC-grade 4 but without any clinical symptoms, it should be reconsidered whether the event is classified as serious. If so, the SAE reporting to the KKS Heidelberg is additionally necessary (see section 9.3). Anyway, if one of the seriousness criteria, e.g. hospitalisation required or life-threatening condition, applies, the SAE reporting is essential.

### 10.1.8 Relationship and outcome of AEs

The investigator and second assessor will evaluate each AE that occurred after administration of Gazyvaro regarding the **relationship** with the administration of Gazyvaro and in this clinical trial also to the radiation therapy:

- Definitely related:** There is a reasonable possibility that the event may have been caused by the IMP/radiation therapy. A certain event has a **strong temporal relationship** and an alternative cause is unlikely.
- Probable:** An AE that has a reasonable possibility that the event is likely to have been caused by the IMP/radiation therapy. The AE has a **timely relationship** and **follows a known pattern of response**, but a potential alternative cause may be present.
- Possible:** An AE that has a reasonable possibility that the event may have been caused by the IMP/radiation therapy. The AE has a **timely relationship** to the IMP; **however, the pattern of response is untypical**, and an alternative cause seems more likely, or there is significant uncertainty about the cause of the event.
- Unlikely:** Only a remote connection exists between the IMP/radiation therapy and the reported adverse event. Other conditions including concurrent illness, progression or expression of the disease state or reaction of the concomitant medication appear to explain the reported adverse event.
- Not related:** An AE that does not follow a reasonable temporal sequence related to the IMP/radiation therapy and is likely to have been produced by the subject's clinical state, other modes of therapy or other known aetiology.
- Not assessable:** There is insufficient or incomplete evidence to make a clinical judgement of the causal relationship.

All subjects who have reportable AEs, whether considered associated with the use of the trial medication or not, must be monitored to determine the **outcome**. The clinical course of the AE will be followed up until resolution or normalisation of changed laboratory parameters or until it has changed to a stable condition. This also holds for on-going AEs/SAEs of withdrawn subjects.

The outcome of an AE at the time of the last observation will be classified as:

- Recovered / resolved:** All signs and symptoms of an AE disappeared without any sequels at the time of the last interrogation.
- Recovering / resolving:** The intensity of signs and symptoms has been diminishing and / or their clinical pattern has been changing up to the time of the last interrogation in a way typical for its resolution.
- Not recovered/not resolved:** Signs and symptoms of an AE are mostly unchanged or worsened at the time of the last interrogation.
- Recovered / resolved with sequel:** Actual signs and symptoms of an AE disappeared but there are sequels related to the AE.
- Fatal:** Resulting in death. If there is more than one adverse event only the adverse event leading to death (possibly related) will be characterised as 'fatal'.

Unknown                      The outcome is unknown or implausible and the information cannot be supplemented or verified.

The action taken with the IMP/radiation therapy will be assigned to one of the following categories:

Dose not changed:    No change in the dose of the IMP/radiation therapy.  
Dose reduced:        Reduction in the dose of the IMP/radiation therapy.  
Dose increased:      Increase in the dose of the IMP/radiation therapy.  
Drug withdrawn:     Discontinuation of the IMP/radiation therapy.  
Unknown:             The information is unknown or implausible and it cannot be supplemented or verified  
Not applicable:      The question is implausible (e.g. the subject is dead).

The term “countermeasures” refers to the specific actions taken to treat or alleviate adverse events or to avoid their sequels. Following categories will be used to categorise the countermeasures to adverse events:

None:                    No action taken.  
Drug treatment:      Newly prescribed medication or change in dose of a medication.  
Others:                 Other countermeasures, e.g. an operative procedure.

## 10.2 Period of Observation and Documentation

Adverse events (AEs) will be ascertained by the investigators using non-leading questions, noted as spontaneously reported by the patients to the medical staff or observed during any measurements on all study days. The observation period begins with the first administration of the Gazyvaro (before the first administration of the Gazyvaro: medical history) and ends with the last study visit, i.e. 30 month after the last take of study medication. AEs will be documented in the patient file and in the CRF. All subjects who present AEs, whether considered associated with the use of the trial medication/radiation therapy or not, will be monitored by the responsible investigator to determine their outcome; this applies to withdrawals too.

The end date of the SAE is defined typically the same as for AEs. The end date of the SAE must not be later than the end date of the corresponding AE.

AEs and SAEs that are on-going at the time of death are considered not resolved or resolving.

All SAEs and their relevance for the benefit/risk assessment of the study will be evaluated continuously during the study and for the final report. All SAEs will be documented in the "Serious Adverse Event" form.

## 10.3 Reporting of Serious Adverse Events by Investigator

All SAEs must be reported by the investigator to the responsible Safety Officer at the KKS Heidelberg **within 24 hours** after the SAE becomes known using the "Serious Adverse Event" form. The initial report must be as complete as possible including details of the current illness and (serious) adverse event and an assessment of the causal relationship between the event and the trial medication/radiation therapy.

The reporting will be performed by faxing a completed ‘SAE Form’ to the KKS Heidelberg, [contact]**

The investigator must also inform the site monitor in all cases.

**[name]**

The 'Second Assessment Form' will contain the following information:

- I) Assessment of relationship between SAE and IMP/radiation therapy (causality)
- II) Assessment of expectedness of SAE (derived from IB)
- III) Statement if the benefit/ risk assessment for the trial did change as a result of SAE.

The expedited reporting (to competent authority, responsible ethics committee and investigators) will be carried out by a responsible Safety Officer at KKS Heidelberg. Only SUSARs occurring after administration of Gazyvaro will undergo expedited reporting.

Details concerning the reporting of SUSARs will be described in a separate document "Safety Manual".

## 10.5 Emergency Treatment

During and following a subject's participation in the trial, the investigator should ensure that adequate medical care is provided to a subject for any AE including clinically significant laboratory values. The investigator should inform a subject when medical care is needed for intercurrent illness(es) of which the investigator becomes aware.

# 11. STATISTICAL PROCEDURES

## 11.1 Number of Patients

Due to the descriptive character of the trial, no assessment of any formal statistical hypotheses is performed. The calculation of the number of patients is primarily based on the aspects of practicability and precision of the results. The following calculations are based on the intention-to-treat (ITT) population. Since the strength of the results for the primary endpoint may be weakened due to early drop-outs (as described later), the number of patients needed should be high enough to compensate for potential drop-outs. Primary endpoint is the rate of metabolic CR in week 18 in patients with initially remaining lymphoma judged by FDG-PET/CT. Based on the morphologic CR rate of 37-84% after 2 x 2 Gy in the literature (see Table 2) and in face of a lack of data for metabolic CR after 2x2 Gy, a CR rate of 60% (about the median of CR in Table 2 and approximately the CR rate in week 18 in the MIR

trial (62%)) is assumed. If fifty patients enter the FDG-PET/CT and the observed metabolic CR rate amounts to 60%, the half width of the asymptotic two-sided 95% confidence interval amounts to about  $\pm 13.5\%$ .

Based on the experience of the MIR trial, a general drop-out rate of 10% is assumed, and about 30% of the included patients are expected to have no remaining lymphoma after initial surgery to prove the histology. In addition, we expect an additional drop-out rate of about 15% after the initial FDG-PET due to stage-shifting in a stage III disease based on the Barrington paper about PET staging [45].

These considerations lead to the following calculation:

If 93 patients are being recruited, about 15% will drop out due to a stage-shift to higher stages after FDG-PET (79 patients remaining). Of these 79 patients, about 30% will have no remaining PET-positive lymphoma after initial surgery (according to the experiences in the MIR trial). Therefore, 55 patients would start therapy with the goal of reaching the primary endpoint assessment. Assuming a drop-out rate of 10%, 50 patients will be available for final assessment of the primary endpoint.

The number of  $n=93$  is at the upper limit of the patients to be included. This number of definitively included patients might drop during the trial (e.g. if less patients show a stage-shift or more patients show remaining lymphoma).

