## STUDY FLOW CHART

Two stage Screening:

- Histology and CT or MRI: centrally approved follicular lymphoma grade 1/2 in clinical stage I/II (max. 93 patients)
- FDG-PET/CT: exclusion of stage III/IV patients (approx. 15%= 14 patients)  
Inclusion of max 79 patients: ca. 70% (=55 patients with remaining lymphoma); approx. 30% (=24 patients with metabolic CR)  
Drop-out-rate: approx. 10% (analyzable for primary endpoint 50 patients with remaining PET positive lymphoma)

\* = centrally reviewed

PET-pos (PET+): PET positive residual lymphoma  
 PET-neg. (PET-): metabolic CR  
 W: week  
 FU: Follow-up examinations  
 morph. SD: morphological SD

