### 5.5.2 Definition of drop-outs

Term	Definition
Drop-out, study	
Participation terminated completely, including follow-up
 
Possible reasons:
 
 
• Patient withdraws consent: Withdrawal
 
• Patient moved/cannot be contacted
 
• Follow-up-interventions cannot be performed due to medical reasons
 
• Non-compliance of patient
 
 
Drop-out after completion of study intervention: Lost to follow-up
 
FU-CRF-forms need to be marked as invalid.
 
Final examination will be performed, if patient agrees. Study-Completion/ Withdrawal-form will be completed.

Drop-out, study intervention	Termination of study intervention, follow-up as per protocol.
Screening-failure	
Exclusion criteria given prior to screening / enrolment:
 
Patient will be recorded at screening list, but will not be provided with a patient number.
 
(Depending on sponsor a screening CRF may have to be completed)

Protocol deviation	
Drop-out to study and drop-out to study intervention are both protocol deviations.
 
It needs to be predefined, how to manage each type of protocol deviation.
 
Major deviations:

If exclusion criteria become evident after enrolment, and safety of the participant is affected, or if the diagnosis does not any more relate to the indication listed in the protocol affecting the benefit/risk negatively, the participant has to be excluded from study intervention. FU-examinations may still be performed.

Minor deviations:

Other protocol deviations (errors in timing of visits/ missing samples/ missing examinations) do not result in exclusion

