## 11.2 Variables of analysis

Primary endpoint is the metabolic complete response (CR) in week 18 in patients with initially remaining lymphoma judged by FDG-PET/CT.

Secondary endpoints are:

- Morphologic CR, PR, SD, PD in week 7, week 18 and month 6 in patients with initially remaining lymphoma judged by CT/MRI
- Historical comparison of the morphologic response with MIR data (using MabThera); the comparison of the CR rate in week 7 would be a comparison of the two different CD20 antibodies. Based on the patient numbers no matched pair analysis will be possible
- Progression-free survival (PFS) of all treated patients (2 years after individual treatment start)
- Toxicity (NCI-CTC criteria, version 4.03) of all patients
- Relapse rate and pattern of recurrence of all treated patients at all follow-up visits.
- Overall survival (OS) of all treated patients (2 years)
- Quality of life according EORTC QLQ C30 and FACT-Lym questionnaires at inclusion and in week 18, month 12, 24 and 30 (all treated patients)
- MRD response: initially, week 18, months 12 and month 24 (all treated patients). MRD is evaluated by the laboratory of [name] (Kiel) using at least the markers: t(14:18) PCR for MBR, 3'mbr, 5'mcr and MCR; clonal IGH rearrangements (FR1-3); clonal IGL rearrangements (IGK and Kappa-KDE)

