## 11.3 Definition of the Trial Populations

All patients, who received at least parts of the treatment defined in this protocol, will be analyzed in the intention-to-treat (ITT) population as well as in the safety population. All patients, who deviated less than 20% from the protocol-defined dose and fulfill all inclusion and exclusion criteria, will be analyzed in the per-protocol (PP) population. Efficacy will be evaluated in the ITT- as well as in the PP population. Toxicity data will be analyzed in safety population.

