## 11.4 Statistical Methods

There will be a descriptive analysis of the data. The rate of metabolic CR in week 18 will be calculated as relative frequency. The related 95% confidence interval will be calculated using the "score method" by Wilson [65]. This method showed excellent performance characteristics as compared to alternative

approaches of constructing confidence intervals for rates [64]. In addition, the rate of metabolic CR will be estimated using the Kaplan-Meier method and the 95% Greenwood confidence interval to take into account a potential influence of censored values. (ITT and PP population)

PFS and OS at 2 years after initiation of the therapy of each patient will be analyzed using the Kaplan-Meier method and the two-sided 95% confidence intervals according to Greenwood. (ITT and PP population).

Remission- and recurrence rates will be calculated as relative frequencies and reported together with the 95% confidence intervals according to Wilson. (ITT and PP population)

Quality of life will be evaluated according to the evaluation guide of the two questionnaires. (ITT and PP population)

Toxicity will be evaluated for frequency and intensity (safety population). Adverse events will be coded by MedDRA (actual version at the time of data base lock). The counts of the events and the counts of patients will be listed in a table. All patients under observation will be taken into account for the calculations of the frequency of recurrences at the respective time.

All statistical procedures will be defined in a statistical analysis plan (SAP), which will be finalized before data base lock. The responsible statistician and the LKP will authorize the SAP.

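### Does the figure of 50 assessable patients in section 11.1 contradict the ITT denominator for the week-18 metabolic CR rate?

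*Combined protocol and SAP*

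**What the plan says.** Section 11.1 (repeated in the synopsis) opens its working with "The following calculations are based on the intention-to-treat (ITT) population". It then narrows 93 recruited patients to 79 after stage shift and to 55 with PET-positive disease: "Therefore, 55 patients would start therapy with the goal of reaching the primary endpoint assessment". The last step is "Assuming a drop-out rate of 10%, 50 patients will be available for final assessment of the primary endpoint". The flow chart carries the same count, "analyzable for primary endpoint 50 patients with remaining PET positive lymphoma". The precision figure is stated conditionally, for fifty patients entering the PET with an observed CR rate of 60%.

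The analysis itself is set out in three places.

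- Section 11.2: "Primary endpoint is the metabolic complete response (CR) in week 18 in patients with initially remaining lymphoma judged by FDG-PET/CT".
- Section 11.3: "All patients, who received at least parts of the treatment defined in this protocol, will be analyzed in the intention-to-treat (ITT) population". No week-18 scan is required for membership.
- Section 11.4: the week-18 CR rate is a relative frequency with a Wilson interval, in ITT and PP. In addition, "the rate of metabolic CR will be estimated using the Kaplan-Meier method and the 95% Greenwood confidence interval", to allow for censoring.

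On incomplete follow-up, section 5.5.2 classes as minor those deviations such as mistimed visits and "missing examinations) do not result in exclusion". Section 5.5.1 asks for a withdrawal examination covering the primary endpoint, if the patient agrees. Section 11.4 leaves the detail to a SAP to be finalized before data base lock.

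**The concern.** The sample-size section claims ITT but works with a set from which drop-outs have been removed. A reader could therefore take the primary denominator to be the scanned patients (50) or the treated patients (55). Section 11.1 says drop-outs are dealt with later, but what follows is a rate and not a rule for classifying them. There is also the withdrawal examination. A patient who leaves before week 18, perhaps before the week-9 radiotherapy, might have a CR on it, and no sentence says whether that CR counts. In an open, single-arm trial whose headline result is one proportion, an unstated denominator leaves room to choose after the outcomes are known.

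**Working it through.** **Inputs.** From section 11.1: 93 recruited, 15% stage shift, 30% without remaining PET-positive lymphoma, 10% drop-out, CR rate 60%, two-sided 95% asymptotic interval. From section 11.4: Wilson interval for the analysis. Assumption for illustration: 30 CRs among the 50 scanned (60%), and 5 treated patients without a week-18 PET.

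**1. The plan's own figures.**
- 93 × 0.85 = 79.05, so 79.
- 79 × 0.70 = 55.3, so 55.
- 55 × 0.90 = 49.5; unrounded, 93 × 0.85 × 0.70 × 0.90 = 49.8, so 50.
- Half-width = 1.96 × √(0.6 × 0.4 / 50) = 0.1358, or 13.6 points, which agrees with the stated value of about 13.5.

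The arithmetic is sound for its stated condition of fifty scanned patients.

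**2. The same precision on the treated set.** 1.96 × √(0.6 × 0.4 / 55) = 0.1295, or 12.9 points. Using 50 overstates the width by about 0.6 points (13.58 − 12.95). This is the cautious direction, and no sample size changes.

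**3. The denominator from sections 11.2 to 11.4.** Section 11.3 admits everyone treated. Section 11.2 restricts the endpoint to those with initially remaining lymphoma. Section 11.4 takes a relative frequency in that set. The planned denominator is therefore the 55 starters. A relative frequency counts the patients with the event, so a patient with no documented week-18 CR stays in the denominator and out of the numerator.

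**4. What the choice is worth.** Wilson limits are [p + z²/2n ± z√(p(1−p)/n + z²/4n²)] / (1 + z²/n), with z = 1.96.

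| Handling of the 5 drop-outs | Rate | Wilson 95% interval |
|---|---|---|
| Left out (scanned only) | 30/50 = 60.0% | 46.2 to 72.4 |
| Counted as non-CR (literal ITT) | 30/55 = 54.5% | 41.5 to 67.0 |
| One early CR counted | 31/55 = 56.4% | 43.3 to 68.6 |
| Two early CRs counted | 32/55 = 58.2% | 45.0 to 70.3 |
| All five counted as CR (extreme) | 35/55 = 63.6% | 50.4 to 75.1 |

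The gap between the first two rows is 60.0 − 54.5 = 5.5 points. From literal ITT to the extreme is 63.6 − 54.5 = 9.1 points. Both are smaller than the planned half-width.

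**5. Early withdrawal examinations.** The endpoint is CR in week 18, and the study schedule gives that visit a window of ±1 week. A CR seen before the window is not a week-18 CR. Section 5.5.1 asks for the examination but does not say that it replaces the week-18 result.

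**The case for a change.** The best opposing argument is about timing. Section 11.4 requires the SAP only before data base lock, planned for Q1 2024, and the trial is open, so the week-18 results will be known well before then. The Kaplan-Meier estimate does not close the gap. If drop-outs are censored before week 18 and CR is first assessed at week 18, it returns the scanned-only value of 60.0%, and two estimates labelled ITT would then differ by 5.5 points. Section 5.5.2 gives limited help, because its wording on missing examinations may refer to exclusion from the intervention and not from the analysis.

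Part of this stands. The plan never says in one sentence that a missing week-18 PET is a non-CR, the ITT label in section 11.1 is loose, and the use of the withdrawal examination is not explained. But the Kaplan-Meier estimate is expressly additional, and its difference from the simple proportion has a plain cause, namely censoring. The group affected may also be smaller than the 10% suggests. Section 5.5.2 separates stopping the intervention, with follow-up continuing as planned, from leaving the study, so a patient who only stops treatment can still have the week-18 scan. Section 5.5.1 is less clear on this, because it also describes adverse-event withdrawals as leaving the study.

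**Conclusion.** No change to the plan follows. The count of 50 in section 11.1 and the flow chart is what remains after a drop-out allowance; neither place says that drop-outs leave the ITT set. The analysis sections read as written give one conventional and conservative primary rate: week-18 CRs over all treated patients with initially remaining lymphoma. A statistician following them would reach a sound result, and the missing sentence is one that a SAP would ordinarily supply.

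At planning values the choice between scanned and treated patients moves the estimate by 5.5 points, against a planned half-width of 13.6. The trial tests no formal hypothesis, so no pass or fail threshold turns on the difference. N, the recruitment funnel and the stated precision all stand. This rests on 5 drop-outs and 30 CRs among 50 scanned; more drop-outs than the assumed 10% would widen the gap, but the denominator rule would be the same.
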